1. PROTOCOL SUMMARY

1.1. Synopsis

Protocol Title:

A Phase 2 study to assess the safety, efficacy of FLX475 combined with Pembrolizumab in patients with advanced or metastatic gastric cancer

Name of Sponsor: Hanmi Pharmaceutical Co., Ltd.

Name of Investigational Product: FLX475, Pembrolizumab

Principal Investigator: [REDACTED]

Publication(s): (if applicable)

Planned Study Period:

The end of study is defined as the date when the last subject, last visit (LSV) occurs or the date at which all required follow-up data and documentation have been received by Sponsor, whichever occurs later. The study is expected to be performed for about 2 years from End of Treatment and the duration may be shorten or extended depending on the study conditions.

Development Phase: 2

Objectives:

To evaluate safety and anti-tumor effect of FLX475 combined with pembrolizumab in subjects with advanced or metastatic gastric cancer. The primary and secondary efficacies will be evaluated by RECIST 1.1 and iRECIST.

Primary Objective:

- To assess the anti-tumor efficacy of FLX475 in combination with pembrolizumab in subjects with advanced or metastatic gastric cancer by RECIST 1.1

Secondary Objectives:

- To assess of the clinical efficacy including Disease Control Rate (DCR), Time to Response (TTR), Duration of Response (DOR) and Progression Free Survival (PFS) by RECIST 1.1
- To assess Overall Survival (OS)
- To assess of the clinical efficacy by iRECIST including iORR, iDCR, iTTR, iDoR, iPFS
- To assess the safety and tolerability of FLX475 combined with pembrolizumab based on Laboratory assessments and Adverse Event (AE), Serious Adverse Events (SAE) using National Cancer Institute Common Terminology Criteria for Adverse Events (NCI-CTCAE) v 5.0

- [REDACTED]
- [REDACTED]
- [REDACTED]
- [REDACTED]

Study Design and Treatment Plan:

This clinical study is a Phase 2, open-label study to assess the efficacy, safety profile of FLX475 combined with pembrolizumab in patients with advanced or metastatic gastric cancer. Approximately 90 subjects may be enrolled across two cohorts to examine the safety and efficacy. This study is designed to assess the potential anti-tumor activity when administered at the 100mg QD of FLX475 with pembrolizumab and will be conducted (2) cohorts as detailed below.

- Cohort 1: Checkpoint inhibitor naïve Epstein-Barr Virus (EBV) negative gastric cancer subjects who have progressed on at least 2 prior systemic treatments for advanced or metastatic gastric cancer
- Cohort 2: Checkpoint inhibitor naïve EBV positive gastric cancer subjects who had at least 1 prior systemic treatment for advanced or metastatic gastric cancer

Cohort 1 will be enrolled in two-stage, starting with at least 10 subjects in the first stage. Expansion to the stage 2 of cohort 1 will be based on the overall safety and efficacy data as well as any available PK and PD data when the 10th subject completes 4 cycles (or 12 weeks; after 2nd response assessment) or withdrawn from the study, whichever occurs first. During this data review, Sponsor can determine study discontinuation if there is no responder from 10 subjects in the first stage. Once expanded, 20 additional subjects will be accrued in stage 2 and further assessment for the safety and efficacy based on the accumulated data up to 30 subjects (10 from stage 1 and 20 stage 2) will be performed. Referring to the published data[11], 15% of ORR is the minimum criteria to proceed for the next stage in the study. If the posterior probability for the ORR $\geq 15\%$ is less than 80%, the enrollment to the cohort will be paused and assessed overall safety along with PK and PD data available. In consideration of the cumulative overall safety and efficacy up to the 30 subjects along with the other competitive landscape, the cohort 1 could be expanded further up to 60 subjects at maximum including the previous subjects enrolled or could be stopped for further enrollment. Also, if required, there could be another stage to investigate further after 2nd stage as well.

Cohort 2 will be enrolled in similar way to the cohort 1 starting with 10 subjects in the first stage and expanded to the second stage based on the overall safety and efficacy as well as available PK and PD data when the 10th subject completes 4 cycles (or 12 weeks; after 2nd response assessment) or withdrawn from the study, whichever occurs first. Referring to the published data[12], for cohort 2 30% of ORR is the minimum criteria to proceed for the next stage in the study. Once determined to the second stage, additional 10 subjects will be enrolled for cohort 2 and If the posterior probability for the ORR $\geq 30\%$ is less than 80%, the enrollment to the cohort will be paused and assess overall safety along with PK and PD data available. If required, further enrollment up to 30 in total as maximum might be performed based on the overall data up to 20 subjects in comparison with the competitive landscape. Also, if required, there could be another stage to investigate further after 2nd stage as well.

The next stage of each cohort will be determined after the comprehensive evaluation from the previous stage by the Independent Data Monitoring Committee(IDMC).

To study potential PD biomarker changes that may be indicative of combined pathway inhibition by the pembrolizumab and FLX475 combination, paired (pre- and post-treatment) tumor biopsies will be obtained from all subjects.

The screening period (Day -30 to Day -1) lasts up to approximately 30 days prior to Cycle 1 Day 1. Patients must meet all Inclusion/Exclusion Criteria to participate in the study. All screened patients will provide written Informed Consent prior to any study procedures.

Once screening procedures are completed and eligibility is confirmed, subjects will start treatment Cycle 1 with FLX475 and pembrolizumab on Day 1. Subject will continue to receive study treatment for an approximate of 2 years (35cycles) or until subject withdrawal from the study, confirmed progression of cancer, intolerable study treatment-related toxicity despite appropriate dose modification and supportive treatment, pregnancy or breastfeeding, substantial noncompliance with study procedures, loss to follow-up, or study termination by the Sponsor, whichever occurs first.

For subjects who have radiological Progressive Disease (PD) by Response Evaluation Criteria in Solid Tumor (RECIST) 1.1 as determined by the investigator will decide whether the subject can continue to receive study treatment until repeat, confirmatory imaging is obtained using modified RECIST for immunotherapies (iRECIST) for subject management.

Number of Subjects:

As stated in the study design part, each cohort will enroll target subjects separately and both cohorts will initiate 2-stage design. Since the study is to explore safety and efficacy by FLX475 and pembrolizumab, the study size is based on feasibility rather than formal testing. The initial number of target subjects for the 1st stage of both cohorts is determined as 10. However, the target subject number for the 2nd stage would be determined based on the overall safety assessment and the posterior probability of at least 80% to achieve the ORR \geq 15% and ORR \geq 30% for cohort 1 and cohort 2, respectively.

The posterior probability for ORR \geq 15% and ORR \geq 30% for cohort 1 and 2, respectively, based on the responses in the first and second stage is described in the Table 11.1:1 and Table 11.1:2 assuming uniform prior distribution for ORR as an example.

- Prior distribution for ORR (P) \sim Unif (0,1)
- Observed data X \sim Binomial (N, P)
- Posterior distribution for ORR (P| X) \sim Beta (1+X, 1+N-X)

For example, if we observed 1 response out of the initial 10 subjects of cohort 1 at 1st stage followed by 6 responses out of additional 20 subjects at 2nd stage, we could assume that the probability of ORR \geq 15% by FLX475 and pembrolizumab combination therapy would be 92% based on the observed data (Table 11.1:1). Also, if we observed 1 response out of the initial 10 subjects of cohort 2 at 1st stage followed by 7 responses out of additional 10 subjects at 2nd stage, we could assume that the probability of ORR \geq 30% by FLX475 and pembrolizumab combination therapy would be 85% based on the observed data (Table 11.1:2). Considering the minimum posterior probability of 80% to achieve the ORR \geq 15% for cohort 1 and \geq 30% for cohort 2 as well as the overall safety data, the total number of subjects for each cohort will be adjusted after each stage.

Criteria for Inclusion/ Exclusion:

Patients eligible for enrolment in the study must meet all of the following criteria:

Inclusion Criteria

Patients meeting all of the following criteria must be enrolled in the study:

1. All patients must have histologically or cytologically confirmed, advanced, relapsed or metastatic gastric or gastroesophageal junction adenocarcinoma.
2. Patient is \geq 18 years of age (or country's legal age of majority if the legal age was $>$ 18 years) at the time of obtaining informed consent.

3. Patient must have one of the following diagnoses to be eligible for enrollment into cohorts:
 - A. Cohort 1: Checkpoint inhibitor naïve Epstein-Barr Virus negative (EBV-) gastric cancer patient who has had a disease progression after at least 2 prior systemic treatments for advanced or metastatic gastric cancer
 - B. Cohort 2: Checkpoint inhibitor naïve Epstein-Barr virus positive (EBV+) gastric cancer patient (as determined by standard methods, e.g. EBER ISH or LMP-1 IHC) who had at least 1 prior systemic treatment for advanced or metastatic gastric cancer
4. Patient has an Eastern Cooperative Oncology Group (ECOG) performance status of 0 or 1 and has a life-expectancy \geq 3 months.
5. Patient's interval from prior to the first study dose is at least 4 weeks for systemic anticancer therapy including investigational agents (or at least 5 half-lives for investigational/ non-cytotoxic agents, whichever is longer. Upon discussion with the Medical Monitor, fewer than stated wash-out period may be allowed provided that the patient has adequately recovered from any clinically relevant toxicity).
6. Patient must have at least one measurable lesion at baseline by computed tomography(CT) or magnetic resonance imaging (MRI) per Response Evaluation Criteria in Solid Tumors (RECIST v1.1) Lesions situated in a previously irradiated area are considered measurable if progression has been demonstrated in such lesions.
7. Demonstrate adequate organ function as defined in Table 1.1:1. All screening labs should be performed within 14 calendar days prior to the first study dose.
8. Patient must be willing and able to provide tissue from a newly-obtained biopsy of a tumor lesion not previously irradiated (unless subsequent progression demonstrated). In addition, patient must be willing to provide a tumor biopsy while on treatment at Cycle 2 day 15 (\pm 3 days) and may be asked to provide additional biopsies at other timepoints such as the time of discontinuation due to progression. Newly-obtained tissue will be from the stomach and/or gastroesophageal junction or a metastatic location. The post-treatment biopsy specimens should be preferred to collected from the same lesion that was biopsied pre-treatment.
Note: Newly obtained is defined as a specimen obtained up to 6 weeks (42 days) prior to initiation of treatment on Day 1 (Cycle 1) and with no additional anti-cancer treatment having been given after the specimen was obtained. To confirm eligibility, preferred to use archival tissue, but newly obtained biopsy specimens may be replaced for patient unable to submit archival tissue samples. Newly-obtained (FFPE block or tissue in formalin solution) or archived specimens (FFPE block) are preferred to slides.
Note: The preferred submitting specimen is the FFPE block. If submitting unstained cut slides, newly cut slides should be submitted to the testing laboratory. Details pertaining to tumor tissue submission can be found in the Laboratory Manual.
9. For female patient of childbearing potential should have a negative serum pregnancy test within 14 calendar days prior to the first study dose.
10. A female participant is eligible to participate if she is not pregnant, not breastfeeding, and at least one of the following conditions applies: a) Not a woman of childbearing potential (WOCBP) b) A WOCBP who agrees to follow contraceptive guidance during the treatment period and for at least 120 days after the last dose of study treatment.

11. For male patient should agree to use 2 adequate methods of contraception, one of which must be a barrier method, from starting at screening and continue throughout the study period and 120 days after the final dose of study treatment.
12. Ability to swallow tablets without difficulty.
13. Signed and dated written Informed Consent Form by the patient.

Exclusion Criteria

Patients meeting any of the following criteria must not be enrolled in the study:

1. Has received prior therapy with an anti-PD-1, anti PD-L1, or anti PD-L2 agent or an agent directed to another stimulatory or co-inhibitory T-cell receptor (e.g., CTLA-4, OX-40, CD137), any history of discontinuing from that treatment due to a Grade 3 or higher immune-related adverse event (irAE).
2. Patient with documented MSI-H status or confirmed by central lab test.
3. Has active autoimmune disease that has required systemic treatment in past 2 years (i.e. with use of disease modifying agents, corticosteroids or immunosuppressive drugs). Replacement therapy (e.g., thyroxine, insulin, or physiologic corticosteroid replacement therapy for adrenal or pituitary insufficiency, etc.) is not considered a form of systemic treatment.
4. History of idiopathic pulmonary fibrosis, organizing pneumonia, drug-induced pneumonitis, idiopathic pneumonitis, (non-infectious) pneumonitis that required steroids, or clinical symptoms of active pneumonitis.
5. Has known active central nervous system (CNS) metastasis and/or carcinomatous meningitis. Patient with previously treated brain metastases may participate provided they are stable (without evidence of progression by imaging at least 4 weeks prior to the first dose of study treatment and any neurologic symptoms have returned to baseline), have no evidence of new or enlarging brain metastases, and are not using steroids for at least 14 days prior to study treatment. This exception does not include carcinomatous meningitis which is excluded regardless of clinical stability.
6. Has a known additional malignancy that is progressing or requires active treatment within the past 2 years. Exceptions include basal cell carcinoma or squamous cell carcinoma of the skin that has undergone potentially curative therapy, in situ cervical cancer or any other cancer that has been in complete remission for ≥ 2 years.
7. Patient has had screening echocardiogram (ECHO) or multiplegated acquisition (MUGA) scan, performed results in a left ventricular ejection fraction (LVEF) that is $< 50\%$.
8. Significant cardiovascular disease, including myocardial infarction, arterial thromboembolism, or cerebrovascular thromboembolism within 6 months prior to start of study treatment, history of cardiac, carotid, or other major cardiovascular surgery, history of valvular heart disease, symptomatic dysrhythmias or unstable dysrhythmias requiring medical therapy, angina requiring therapy, symptomatic peripheral vascular disease, clinically significant history of syncope, New York Heart Association (NYHA) Class 3 or 4

congestive heart failure, or chronic Grade 3 hypertension (diastolic blood pressure \geq 100 mmHg or systolic blood pressure \geq 160 mmHg).

9. Significant screening electrocardiogram (ECG) abnormalities including atrial fibrillation (unstable or newly diagnosed), double (left and right) bundle branch block, second degree atrioventricular block type II, third-degree atrioventricular block, Grade \geq 2 bradycardia, QTcF interval \geq 450 msec, PR interval $>$ 220 msec, or unstable cardiac arrhythmia requiring medication. Chronic asymptomatic atrial fibrillation stably controlled with medications is permitted.
10. Known family history of sudden cardiac death.
11. Ongoing risk for bleeding due to cancer or bleeding diathesis.
12. Evidence of an ongoing, uncontrolled systemic bacterial, fungal, or viral infection or an uncontrolled local infection requiring therapy at the time of start of study treatment.

Note: Patient with localized fungal infections of skin or nails are eligible.

13. Has a known history of Human Immunodeficiency Virus (HIV) infection or patient who are HIV seropositive. No HIV testing is required unless mandated by local health authority.
14. Current known active infection of Hepatitis B (defined as HBsAg+ and/or HBeAg+) and high titer of HBV DNA or Hepatitis C virus (defined as Anti-HCV and HCV RNA (+)) infection.
15. Diagnosis of immunodeficiency or is receiving chronic systemic steroid therapy (at doses exceeding 10 mg daily of prednisone equivalent) or any other form of immunosuppressive therapy within 14 days prior to the first dose of study treatment.
16. Has received a live or live-attenuated vaccine within 30 days of planned start of study treatment.

Note: Administration of killed vaccines are allowed.

17. Has had an allogeneic tissue/solid organ transplant.
18. Males who plan to father children within the projected duration of the study, starting with the screening visit through 120 days after the final dose of study treatment.
19. Major surgery within 28 days (or inadequate recovery from the toxicity or complications of the intervention) before the start of study treatment.

Note: If the participant had major surgery, the participant must have recovered adequately from the procedure and/or any complications from the surgery prior to starting study intervention.

20. Radiotherapy within 14 days of start of study treatment. Patient must have recovered from all radiation-related toxicities, not require corticosteroids, and not have had radiation pneumonitis. A 7-day washout is permitted for palliative radiation (i.e., \leq 14-day course of radiotherapy) to non-CNS lesions.
21. Patient currently receiving treatment with any medications that have the potential to prolong the QT interval and that cannot be either discontinued or substituted with a different medication prior to starting study treatment.
22. Patient currently receiving treatment with strong cytochrome P450 (CYP)3A4 inhibitors or inducers should discontinue such treatment or be switched to a different medication prior to starting study treatment.

23. Current participations in another study of an investigational agent or investigational device within 4 weeks prior to the first dose of study treatment.
24. Any illness, medical condition, organ system dysfunction, or social situation, including mental illness or substance abuse, deemed by the investigator to be likely to interfere with a patient's ability to sign informed consent, adversely affect the patient's ability to cooperate and participate in the study, or compromise the interpretation of study results.

Test Product, Dose and Mode of Administration:

█ FLX475 100 mg for oral administration is provided as tablets. All subjects will take FLX475 with water orally once daily (QD) at approximately the same time each day.

Pembrolizumab 200 mg will be administered as an IV infusion over 30 minutes on Day 1 of every 3-week treatment cycle (i.e., every 21 days [\pm 3 days]).

On days when pembrolizumab is also administered (i.e., Day 1 of each cycle), FLX475 should be taken approximately 1 hour before the pembrolizumab infusion.

Duration of Treatment:

Subjects may continue to receive study therapy until the earliest of the following: subject withdrawal from study, confirmed progression of cancer, intolerable study-drug-related toxicity despite appropriate dose modification, the development of intercurrent illness that precludes continued study therapy, pregnancy or breastfeeding, substantial noncompliance with study procedures, completion of Treatment Phase comprising up to 35 treatment cycles for FLX475 and an approximate of 2 years' treatment (35 doses) for pembrolizumab, or study discontinuation.

Criteria for Evaluation:

Efficacy will be assessed according to the RECIST version 1.1 and iRECIST

Safety and tolerability will be assessed using CTCAE version 5.0

Primary Endpoint:

- Objective Response Rate (ORR) by RECIST 1.1

Secondary Endpoints:

- Efficacy in accordance with RECIST 1.1: DCR, TTR, DOR, PFS
- Efficacy in accordance with iRECIST: iORR, iDCR, iTTR, iDOR, iPFS
- Efficacy: OS
- Safety and tolerability: AEs, Laboratory assessments (including hematology, biochemistry, coagulation, urinalysis, vital signs, physical examination, ECG and ECOG)

Statistical Methods:

Treated Set will include all subjects who received at least one dose of study drug (FLX475 or pembrolizumab). All demographics, Baseline characteristics, efficacy and safety data will be analyzed using the Treated Set as a primary analysis population. Tumor Evaluable Set will include all subject

who are enrolled, complete at least one cycle of investigational drug, and is evaluable for tumor response based on RECIST, version 1.1, and will be used for supportive efficacy analysis.

In general, all data will be summarized with descriptive statistics (number of subjects, mean, standard deviation, minimum, median and maximum) for continuous endpoints, and frequency and percentage for categorical endpoints unless other specified. As each cohort will enroll target subjects separately and so the analyses will be performed separately by cohort as well. The data summaries will be presented by stage and overall across stages for each cohort.

Efficacy analysis will be conducted based on Treated Set and Tumor Evaluable Set. Tumor-related endpoints will be analyzed based on investigator's assessment using RECIST version 1.1, and the result from assessment using iRECIST also be presented.

The primary efficacy endpoint is Objective Response Rate (ORR) defined as the proportion of subjects whose confirmed best overall response is either Complete Response (CR) or Partial Response (PR) according to RECIST version 1.1. For the efficacy endpoints such as ORR and DCR, frequency and percentage of subjects who have achieved a response will be summarized by stage and 95% 2-sided confidence interval will be calculated by Clopper-Pearson method.

Time-to-event endpoints, including TTR, DoR, PFS and OS, will be summarized descriptively and graphically using Kaplan-Meier (KM) methodology.

According to iRECIST, Best Overall Response (iBOR) of complete response (CR/iCR), partial response (PR/iPR), stable disease (SD/iSD), Progressive disease (iPD) or unevaluable (iUE) will be derived. iORR, iDCR, iTTR, iDoR and iPFS will be analyzed in the same manner as used analyses in accordance with RECIST 1.1.

OS is defined as the duration of time from the treatment start date to time to death from any cause.

The Statistical Analysis Plan (SAP) will include a more technical and detailed description of the statistical analyses.

Extension Part:

The extension part will provide continued access to FLX475 combined with pembrolizumab to subjects who have previously participated in HM-CCRI-201 study and are ongoing from the treatment with clinical benefit.

The primary objective of the extension part mainly is to provide continued treatment with FLX475 combined with pembrolizumab without the previous study procedures that intended to collect data for further analysis (e.g. efficacy, safety, biomarker, etc.).

Detailed information on Extension part are described in Section [17](#).

Table 1.1:1 Adequate Organ Function Laboratory Values

System	Laboratory Value
Hematology	
Absolute neutrophil count (ANC)	$\geq 1,500/\mu\text{L}$
Platelets	$\geq 100,000/\mu\text{L}$
Hemoglobin	$\geq 9.0\text{ g/dL}$ or $\geq 5.6\text{ nmol/L}$ ^a
Renal	
Creatinine OR Measured or calculated ^b creatinine clearance (GFR can also be used in place of creatinine or CrCl)	$\leq 1.5\text{X}$ upper limit of normal (ULN) OR $\geq 30\text{ mL/min}$ for subject with creatinine levels $> 1.5\text{ X}$ institutional ULN
Hepatic	
Total bilirubin	$\leq 1.5\text{X}$ ULN
AST (SGOT) and ALT (SGPT)	$\leq 2.5\text{X}$ ULN ($\leq 5\text{X}$ ULN for subjects with liver metastases)
Coagulation	
International normalized ratio (INR) OR Prothrombin time (PT) Activated partial thromboplastin time (aPTT) OR partial thromboplastin time (PTT)	$\leq 1.5\text{X}$ ULN unless subject is receiving anticoagulant therapy, as long as PT or aPTT/PTT is within therapeutic range of intended use of anticoagulants

a. Criteria must be met without erythropoietin dependency and without packed red blood cell transfusion within the previous 2 weeks.

b. Creatinine clearance (CrCl) should be calculated per institutional standard.

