6. STUDY POPULATION

6.1. Inclusion Criteria

Patients meeting all of the following criteria must be enrolled in the study:

1. All patients must have histologically or cytologically confirmed, advanced, relapsed or metastatic gastric or gastroesophageal junction adenocarcinoma.
2. Patient is ≥ 18 years of age (or country's legal age of majority if the legal age was > 18 years) at the time of obtaining informed consent.
3. Patient must have one of the following diagnoses to be eligible for enrollment into cohorts:
 - A. Cohort 1: Checkpoint inhibitor naïve Epstein-Barr Virus negative (EBV-) gastric cancer patient who has had a disease progression after at least 2 prior systemic treatments for advanced or metastatic gastric cancer
 - B. Cohort 2: Checkpoint inhibitor naïve Epstein-Barr virus positive (EBV+) gastric cancer patient (as determined by standard methods, e.g. EBER ISH or LMP-1 IHC) who had at least 1 prior systemic treatment for advanced or metastatic gastric cancer
4. Patient has an Eastern Cooperative Oncology Group (ECOG) performance status of 0 or 1 and has a life-expectancy ≥ 3 months.
5. Patient's interval from prior to the first study dose is at least 4 weeks for systemic anticancer therapy including investigational agents (or at least 5 half-lives for investigational/ non-cytotoxic agents, whichever is longer. Upon discussion with the Medical Monitor, fewer than stated wash-out period may be allowed provided that the patient has adequately recovered from any clinically relevant toxicity).
6. Patient must have at least one measurable lesion at baseline by computed tomography(CT) or magnetic resonance imaging (MRI) per Response Evaluation Criteria in Solid Tumors (RECIST v1.1) Lesions situated in a previously irradiated area are considered measurable if progression has been demonstrated in such lesions.
7. Demonstrate adequate organ function as defined in Table 1.1:1. All screening labs should be performed within 14 calendar days prior to the first study dose.

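### The hemoglobin row of Table 1.1:1 pairs 9.0 g/dL with 5.6 nmol/L, limits about a million-fold apart; the printed numbers agree only if the molar unit is mmol/L

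*Protocol*

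**What the plan says.** Table 1.1:1 (Protocol, Section 1.1) lists the laboratory values that define adequate organ function. Its hemoglobin row gives two limits joined by *or*: "\geq 9.0\text{ g/dL}$ or $\geq 5.6\text{ nmol/L". Footnote a to that row adds a further condition: "Criteria must be met without erythropoietin dependency and without packed red blood cell transfusion within the previous 2 weeks".

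The table is binding. Inclusion criterion 7, in the synopsis and again in Section 6.1, requires the patient to "Demonstrate adequate organ function as defined in Table 1.1:1". Section 6.1 gives no hemoglobin limit of its own, and nothing else in the protocol or SAP restates or corrects the row.

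Two further statements bear on which units may be in use. Protocol Section 9.2.5 has the safety laboratory tests done at each site's local laboratory. SAP Section 13.2 expects units to differ between laboratories and converts results to SI units for the summaries.

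**The concern.** A limit given in a mass unit and a molar unit for the same analyte should describe the same concentration. Here the number 5.6 is what the conversion of 9.0 g/dL gives in mmol/L, but the unit beside it is nmol/L. If both halves are taken at face value, a patient who fails the mass limit can still meet the molar one.

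The row is an entry safety threshold. The trial enrolls patients with advanced gastric cancer, asks for a tumor biopsy before treatment and another on treatment (inclusion criterion 8), and excludes ongoing bleeding risk (exclusion criterion 11). Because local laboratories may report in different units, the molar half of the row could be used, and a site working in molar units has no correct limit printed for it.

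**Working it through.** **Inputs from the protocol.** The limits 9.0 g/dL and 5.6 nmol/L, from Table 1.1:1.

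**Assumed input.** The documents give no molar mass. I assume 16,000 to 16,125 g/mol per hemoglobin monomer, with 16,114.5 as a working value, and use the whole tetramer at 64,458 g/mol as the alternative.

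**Formula.** Concentration in mol/L = (g/dL × 10) / molar mass in g/mol. For 9.0 g/dL the numerator is 90 g/L.

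**Step 1: convert 9.0 g/dL and compare it with the printed 5.6 nmol/L.**

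| Molar mass (g/mol) | 9.0 g/dL in mmol/L | 9.0 g/dL in nmol/L | Ratio to 5.6 nmol/L |
|---|---|---|---|
| 16,000 (monomer, low) | 90/16,000 → 5.625 | 5,625,000 | 1,004,464 |
| 16,114.5 (monomer) | 90/16,114.5 → 5.585 | 5,585,032 | 997,327 |
| 16,125 (monomer, high) | 90/16,125 → 5.581 | 5,581,395 | 996,678 |
| 64,458 (tetramer) | 90/64,458 → 1.396 | 1,396,258 | 249,332 |

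The printed pair is not reproduced under either convention. Under the monomer convention the converted value rounds to 5.6 in mmol/L. Under the tetramer convention 5.6 mmol/L would be 36.1 g/dL, so the two printed numbers agree only as monomer mmol/L.

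**Step 2: convert back.** 5.6 nmol/L × 16,114.5 / 10 = 0.000009 g/dL, which is no practical lower limit.

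**Step 3: apply the row literally (monomer, 16,114.5 g/mol).**

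| Hemoglobin (g/dL) | In nmol/L | Meets ≥ 9.0 g/dL | Meets ≥ 5.6 nmol/L | In mmol/L |
|---|---|---|---|---|
| 3 | 1,861,677 | no | yes | 1.86 |
| 5 | 3,102,796 | no | yes | 3.10 |
| 7 | 4,343,914 | no | yes | 4.34 |
| 8 | 4,964,473 | no | yes | 4.96 |
| 8.9 | 5,522,976 | no | yes | 5.52 |
| 9.0 | 5,585,032 | yes | yes | 5.585 |

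Taken as a true alternative, the nmol/L half admits every value tried. If the molar unit is read as mmol/L, the values from 3 to 8.9 g/dL fail both halves. At 9.0 g/dL the patient qualifies on the mass half, and the gap between 5.585 and 5.6 is rounding.

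**The case against.** The strongest objection is that the point may not exist on the source page. It rests on a single letter in a table cell of text extracted from a PDF. The extraction is imperfect elsewhere: the ECG row of Table 1.2:1 is labeled differently from its own footnote g. The hemoglobin row appears only once, so no second copy can confirm the letter. This stands, and it is why the fix begins with the source page.

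A reader might go further and infer that the criterion as written excludes no one. The documents do not support that, for two reasons. First, footnote a still excludes erythropoietin-dependent and recently transfused patients whatever their hemoglobin value. Second, the lower-case *or* most naturally gives one limit in two reporting units. Where the same table offers genuinely alternative tests (creatinine or creatinine clearance, INR or prothrombin time), it uses a capital *OR*. A site reporting in g/dL would simply apply 9.0.

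A reader might also infer that a site reporting in mmol/L would admit a severely anemic patient. That site would have to multiply its result by one million before comparing it with 5.6. More probably it would compare its own number with 5.6 directly, which is the matching figure in mmol/L. A mis-programmed edit check is possible, but it is not documented: Protocol Section 12.2 mentions electronic consistency checks without describing one for hemoglobin.

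There are other safeguards too. Section 8.1.2 sends each eligibility packet to the medical monitor and sponsor for approval before a subject number is assigned. Exclusion criterion 11 covers bleeding risk, and criterion 24 leaves room for the investigator's judgment. These lower the risk but do not correct the row.

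**Conclusion.** As the text stands, the two hemoglobin limits disagree by about a factor of one million: 0.997 to 1.004 million under the assumed monomer masses, and about 249,000 under the tetramer mass. The disagreement does not depend on the convention chosen. What is lost is the lower bound on the hemoglobin value, and only if the nmol/L half is applied literally; the rest of the criterion remains in force. It is a wrong figure in a binding entry criterion with low practical risk, and it is conditional on the source page printing nmol/L. No sample-size figure, posterior probability or planned analysis uses this limit. The arithmetic shows that the row is inconsistent with itself; it does not address which hemoglobin level is clinically appropriate.

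**What to change.** 1. Check the hemoglobin row of Table 1.1:1 on the source page. If it prints mmol/L, nothing needs to change.
2. If it prints nmol/L, the sponsor should reconcile the two halves of the row so that they express the same hemoglobin level.
3. Confirm that any eligibility worksheet, eCRF check or IWRS check built from the table carries the reconciled unit.

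The cost is one unit in one table, made through the protocol's amendment process, plus a look at the eligibility tools. The SAP needs no change.
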